Aim #2: To determine acute and short-term tolerability of cannabis from a neuropsychiatric standpoint. For this aim, repeated neurocognitive and psychiatric assessments will be performed. **Hypothesis #2:** Smoking medicinal cannabis will result in impairment on cognitive measures of attention, concentration, and memory in addition to adverse neuropsychiatric features as measured by the Brief Symptom Inventory, the Subjective Ratings of High and Sedation - Revised, and UKU Side Effect Rating Scale.

Aim #3: To determine the short-term effects of smoked cannabis on global functioning and quality of life in MS. **Hypothesis #3:** Smoking medicinal cannabis will result in improvement in global abilities and quality of life as measured by the Multiple Sclerosis Quality of Life-Inventory.

B. BACKGROUND AND SIGNIFICANCE.

Spasticity is a common and disabling symptom for many patients with MS. It tends to affect the lower extremities more than the upper extremities and associated signs include increased muscle tone, contractures, impaired dexterity, and spontaneous muscle spasms. Spasticity not only produces discomfort for patients but may greatly interfere with their functioning by compromising independence in activities of daily living. Physiotherapy, including passive range-of-motion exercises and stretching, is an essential component of anti-spasticity regimens; however, physical measures alone are usually insufficient. In most patients, adjunctive pharmacologic therapy with agents such as baclofen, benzodiazepines, and tizanidine is usually

Appendix to: [name], [name], [name], et al. Smoked cannabis for spasticity in multiple sclerosis: a randomized, placebo-controlled trial. *CMAJ* 2012. DOI:10.1503/cmaj110837.

Copyright © 2012 Canadian Medical Association or its licensors

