Spasticity Scale, Timed 25-ft Walk, Visual Analog Scale of Pain, cognitive battery, neuropsychiatric assessments, and treatment-emergent effects, beginning 30 minutes after their treatment session. On the last day of the protocol, **Day #17**, the patients will return to the CRC for their third treatment of Phase II. Blood will be drawn for total THC. Patients will undergo assessment with the Modified Ashworth Spasticity Scale, Timed 25-ft Walk, Visual Analog Scale of Pain, cognitive battery, and neuropsychiatric assessments. Following completion of the third treatment, blood will be drawn for peak THC levels, and patients will be assessed with the Modified Ashworth Spasticity Scale, Timed 25-ft Walk, Visual Analog Scale of Pain, cognitive battery, neuropsychiatric assessments, treatment-emergent effects, and MSQL-I beginning 30 minutes after their treatment session.

2. Study Site

The study will be performed at the UCSD La Jolla Clinical Research Center. The CRC is a self-contained organized research unit that is fully staffed by nursing, dietary and core laboratory personnel to support the clinical research project described herein. A room will be equipped with a Tepco 750 smoke scrubber or a HEPA filter (BioSafety, RS 1000).

3. Subjects

We estimate that 30 subjects will be necessary (see Section 7) in this crossover design and therefore plan to enroll 36 MS subjects, expecting attrition of up to 6 subjects over the course of the study. MS patients will be obtained through the UCSD MS Clinic and/or the private practices of their neurologists. These patients will have received extensive neurological evaluation and represent a well-studied MS patient population. MS patients will be solicited by [name], and contacted for appointment by the Research Coordinator. Patients of all ethnic and racial backgrounds are eligible. Prior use of cannabis is not required. Patients will be allowed to continue other currently available treatments for spasticity other than benzodiazepines, if they have been on a stable dose of the medication for at least three months.

3.a. Inclusion Criteria

Subjects will be included if they:

- Have clinically definite or probable, laboratory-supported MS; are between the ages of 18-65

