A placebo-controlled design will be used to diminish the potential for bias in the ascertainment of assessment outcomes. The use of the placebo control will also enable accurate estimates of the side effects of smoked cannabis, which would be necessary to any scientific consideration of its widespread use for treatment of spasticity. Placebo cigarettes will be available from NIDA and will be made from whole plant with the cannabinoids removed. This does not result in any changes in taste, therefore making it difficult by this means alone to distinguish between active-THC and placebo cannabis cigarettes.

Storage and dispensing. Cannabis and placebo cigarettes will be received, stored and dispensed by the pharmacy service at the UCSD CRC. Accountability records will be maintained according to policies and procedures for both Schedule I and investigational drugs. The final disposition of each dose will be recorded. Residual drug supplies will be disposed of as directed by NIDA. Storage of the cannabis and placebo cigarettes will be maintained as directed by NIDA. The cigarettes will arrive frozen from the University of Mississippi. They will be stored in a padlocked freezer, in a research pharmacy, which is locked. Only the licensed pharmacists listed on the DEA registration will have access to the freezer where the cannabis and placebo cigarettes are stored. Any and all additional security precautions dictated by NIDA or other institutional officials will be instituted to be in complete compliance before the start of the study. Dispensing of the cannabis and placebo cigarettes will occur in compliance with NIDA, DEA and FDA regulations.

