Hypothesis #2: Smoking medicinal cannabis will result in impairment on cognitive measures of attention, concentration, and memory in addition to adverse neuropsychiatric features as measured by the Paced Auditory Serial Addition Test, Brief Symptom Inventory, Perceived Deficits Questionnaire, Modified Fatigue Impact Scale, the Subjective Ratings of High and Sedation - Revised, and UKU Side Effect Rating Scale. Means and bootstrap-based bias-corrected confidence intervals will be computed for each assessment time of each specified measure. For each subject the response is the change between a before-after placebo difference and a before-after treatment difference on the specified measures where before and after treatment measurements were taken (e.g. PASAT), and a change between the post-placebo and post-active scores when only the post-treatment measurements were taken (e.g. SRHS-R). We will evaluate the aggregate differences using a one-sample t-test (i.e. perform a paired-sample t-test). Here again we define as clinically important any departure from zero in the hypothesized direction that is greater than one standard deviation of paired differences. In

Appendix to: [name], [name], [name], et al. Smoked cannabis for spasticity in multiple sclerosis: a randomized, placebo-controlled trial. *CMAJ* 2012. DOI:10.1503/cmaj110837.

Copyright © 2012 Canadian Medical Association or its licensors

addition the relationship between total plasma THC and cognitive, neuropsychiatric and treatment-emergent effect scores will be examined using Pearson correlation.

Hypothesis #3: Smoking medicinal cannabis will result in improvement in global abilities and quality of life as measured by the Multiple Sclerosis Quality of Life-Inventory. For each subject the response is the change between a post-placebo and a post-treatment score on the MSQOL-I. The aggregate differences will be evaluated using a one-sample t-test (i.e. perform a paired-sample t-test).

Regression and covariate analysis will also be applied to determine the association between the major efficacy/safety outcomes and important clinical variables such as EDSS score, smoking history, exhaled CO levels, concomitant medications, etc.

E. HUMAN SUBJECTS

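### The Hypothesis #2 paired test leaves out patients without scores under both products, chiefly cannabis-first patients who stop before Phase II, and no stated analysis counts stopping for intolerance

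*Protocol*

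**What the plan says.** Aim #2 is "To determine acute and short-term tolerability of cannabis from a neuropsychiatric standpoint". Section D.8, Hypothesis #2, defines the response in two ways. For measures taken before and after smoking, such as the PASAT, it is "the change between a before-after placebo difference and a before-after treatment difference on the specified measures where before and after treatment measurements were taken". For measures taken only afterwards, it is "a change between the post-placebo and post-active scores when only the post-treatment measurements were taken (e.g. SRHS-R"). The test follows: "We will evaluate the aggregate differences using a one-sample t-test (i.e. perform a paired-sample t-test"). Clinical importance is set on the same scale, as "any departure from zero in the hypothesized direction that is greater than one standard deviation of paired differences".

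Section D.3 says that 30 patients are needed and that the investigators "therefore plan to enroll 36 MS subjects, expecting attrition of up to 6 subjects over the course of the study". Section E tells participants that they may leave at any time, and lets an interview be ended when a participant is too distressed or fatigued.

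The protocol also plans material that is not tied to pairs. Section D.8 gives means with bootstrap intervals at each assessment time. The visit schedule in D.1 records adverse events in both phases, and D.6 has UKU and SRHS-R ratings after every treatment. No stated analysis uses stopping because of side effects as an outcome.

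**The concern.** A paired response exists only for a patient scored under both products. In an efficacy comparison this is a familiar loss of information. In a tolerability comparison the reason for a missing score can be the effect being measured. Section E lists mood, memory and cognition effects among the risks of inhaled cannabis, and D.5 prepares patients for effects they may find disturbing.

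A cannabis-first patient who leaves for such a reason during Phase I or the washout has a cannabis score and no placebo score, so that reaction is absent from the formal Aim #2 result. The loss selects on the outcome and falls mainly on one sequence. Its direction is known: it makes cannabis look milder. At stake is whether the test and the one-SD criterion can bear the tolerability conclusion unaided.

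**Working it through.** **The plan's own figures.** Enrolment: 30 / (1 − 6/36) = 36, as D.3 states. (Section E says 30 will be enrolled; I use D.3 because it carries the attrition allowance.) Power is stated only under Hypothesis #1, as well over 80% for 30 patients, one SD and alpha 0.05. The noncentral t with 29 degrees of freedom and noncentrality 1 × √30 = 5.48 gives 99.96% two-sided and 99.99% one-sided, so the statement is correct. Even 24 pairs give 99.7%. At one SD the issue is therefore bias and not power.

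**Who has a response.**
- Cannabis-first, stops before Phase II: cannabis scores only, so no response.
- Cannabis-first, stops after a scored placebo session: scores under both products, so can enter.
- Placebo-first, stops after at least one scored cannabis session: scores under both, so can enter, unless the rule for combining the three days of a phase (not stated) requires every session.
- Placebo-first, stops with no score after cannabis, for instance because the interview was ended: no response.

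The gap lies chiefly in the first group.

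**Size.** Assumptions, none of them from the protocol: *m* = 3 to 6 of 36 patients are intolerant; their paired difference exceeds that of the others by Δ = 1 to 2 SD; sequences are split 1:1; only the cannabis-first half of the intolerant patients is lost.

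Understatement of mean harm = Δ × (share intolerant among all − share intolerant among those in the test).

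- *m* = 3, 1.5 lost on average: 3/36 = 8.3%; 1.5/34.5 = 4.3%; difference 4.0 points; × 1 SD = 0.04 SD.
- *m* = 6, 3 lost on average: 6/36 = 16.7%; 3/33 = 9.1%; difference 7.6 points; × 2 SD = 0.15 SD.
- Upper bound, all 6 intolerant and all 6 lost: 16.7% − 0 = 16.7 points; × 2 SD = 0.33 SD.

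**Cross-check under harsher selection.** Simulation of 40,000 trials of 36 normal paired differences, 18 of them cannabis-first, removing the worst-affected patients before the t-test:

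| Loss | Fall in mean | Detection of a true 0.5 SD harm |
|---|---|---|
| None | 0 | 83% |
| 6 at random | 0 | 75% |
| 3 worst cannabis-first | 0.13 SD | 60% |
| 6 worst cannabis-first | 0.21 SD | 38% |
| 6 worst of all | 0.29 SD | 32% |

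With a true harm of 1 SD the test still succeeds in at least 98.9% of trials. The mean among those retained falls to 0.79 to 0.87 of the original SD when the losses are cannabis-first, and to 0.71 when the 6 worst of all are lost. The SD of the retained pairs shrinks too, so the ratio judged against the threshold falls by less.

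**The case against.** A reader might infer that the protocol judges tolerability on completers alone, or that every patient who stops because of cannabis disappears. The documents support neither.

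- The means at each assessment time are not restricted to patients with both phases. Adverse events and UKU ratings are taken at the sessions themselves, so a patient who leaves after one cannabis cigarette will usually have left scores.
- A placebo-first patient scored after one cannabis session can still enter the test.
- It is also tempting to set a possible 6 of 36 intolerant against none among 30 completers. That comparison fails: the paired test compares mean scores and estimates no stopping rate, and intolerant placebo-first patients would mostly remain in it.

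Three further objections have weight. D.3 gives no reasons for attrition, and D.1 creates other losses through toxicology exclusions on Day 1 and Day 15. Safety sets, adverse-event tables and missing-data rules commonly sit in an SAP, so their absence here is no finding. And the remark in D.4 that "The use of the placebo control will also enable accurate estimates of the side effects of smoked cannabis" justifies having a placebo; it promises nothing about patients who leave.

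All of this narrows the point without removing it. The response, the test and the threshold are fixed in the protocol, and together they exclude one-period patients from the formal result for a tolerability aim. The descriptive means contain no contrast of the products and do not register that a patient stopped.

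**Conclusion.** The point holds for the formal Hypothesis #2 result, not for all tolerability reporting. The paired test and its one-SD threshold omit patients without scores under both products, chiefly cannabis-first patients who stop before Phase II, and no stated analysis counts stopping for intolerance. If those stops are due to cannabis, the bias favours cannabis.

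The illustrative size is 0.04 to 0.15 SD, with 0.33 SD as the upper bound if every planned loss is of this kind. These figures rest on assumed numbers of intolerant patients, an assumed excess of 1 to 2 SD and an assumed 1:1 split of sequences. If attrition turns out unrelated to cannabis effects, there is no bias of this sort, only some loss of precision. The point merits a change to the text because the remedy is cheap. It is no reason to abandon the within-patient comparison.

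**What to change.** Keep the paired comparison of cognitive, BSI, SRHS-R and UKU scores. Add to Section D.8:

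1. A tolerability summary by product, reported with equal standing beside the paired test. It covers every patient who smoked at least one study cigarette of that product, not counting the practice session (which uses placebo for everyone). It gives UKU incidence and severity, adverse events, and withdrawals with reason, each withdrawal attributed to the product last smoked.
2. For the score outcomes, an analysis of all available scores, for example a mixed model with treatment, period and sequence, so that one-period patients contribute. This recovers only part of the loss: such patients add between-patient information, and the model assumes that what is missing can be predicted from the scores observed. The withdrawal count in item 1 covers patients who left no usable score.

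Sections D.3 and E should also agree on whether 36 or 30 are enrolled, since that sets the denominator for attrition.

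The cost is a few sentences, one table and one further model. No patients or visits are added. The only new data item may be the reason for withdrawal. The price to the sponsor is a tolerability figure that may look less favourable.

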Treatment Emergent Effects of cannabis will be assessed after each treatment by interview and self-report of physical and psychological symptoms using the Subjective Ratings of High and Sedation - Revised (SRHS-R) and the UKU Side Effect Rating Scale. The **Subjective Ratings of High and Sedation - Revised** has been adapted from Block, et al (1998) for use in the present study to evaluate the subjective effects of cannabis. This scale consists of 10 ratings of different aspects of stimulation vs. sedation (alert/drowsy, attentive/dreamy, tense/relaxed, interested/bored, capable/incompetent, excited/calm, clear-headed/fuzzy, well-coordinated/clumsy, quick-witted/mentally slow, and energetic/lazy). The **UKU Side Effect Rating Scale** is a semi-structured interview that evaluates a wide range of unwanted side effects including psychological (eg, concentration difficulties, failing memory, lassitude), neurological (eg, hypokinesia, paraesthesias), autonomic (eg, accommodation disturbance, orthostatic dizziness, nausea, sweating), and miscellaneous effects (eg, weight gain, diminished sexual desire) (Lingjaerde et al 1986). Each treatment emergent symptom is defined on a four-point scale of intensity (0 = not present; 3 = severe), and rated separately with regard to being causally related to the study drug (improbably related, possibly related, probably related). In addition, sitting and standing blood pressure, heart rate, respirations, and oral temperature will be obtained before

Appendix to: [name], [name], [name], et al. Smoked cannabis for spasticity in multiple sclerosis: a randomized, placebo-controlled trial. *CMAJ* 2012. DOI:10.1503/cmaj110837.

Copyright © 2012 Canadian Medical Association or its licensors

drug administration and at 0.5, 1 and 2 hours after administration to monitor the subject's health status as well as to quantify cannabis's general effects.

Quality of Life (administered at the beginning and end of each phase):

The **Multiple Sclerosis Quality of Life-Inventory** is both a generic and an MS-specific quality of life measure (Coulthard-Morris, 2000). It consists of 138 items and 10 separate scales that assess the following domains: general health status, fatigue, pain, sexual satisfaction, bladder control, bowel control, vision, cognitive function, mental health, and social support. It is self-administered and takes about 30 minutes to complete.

7. Laboratory Assessments

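### Hypothesis #2 judges tolerability by mean-score t-tests and a one-SD importance rule, with no interval for the cannabis-minus-placebo contrast, so the plan never states how much harm remains compatible with the data

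*Protocol*

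**What the plan says.** All references are to the protocol. Section A sets Aim #2 as "To determine acute and short-term tolerability of cannabis from a neuropsychiatric standpoint". The matching hypothesis in Section D.8 predicts harm: "Smoking medicinal cannabis will result in impairment on cognitive measures of attention, concentration, and memory in addition to adverse neuropsychiatric features".

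For that hypothesis Section D.8 fixes four things:

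- **Response.** A placebo-versus-active contrast of before-after changes where both were measured; otherwise "a change between the post-placebo and post-active scores when only the post-treatment measurements were taken (e.g. SRHS-R"). The visit schedule places treatment-emergent effects after treatment only, so the UKU falls under the second form.
- **Test.** "We will evaluate the aggregate differences using a one-sample t-test (i.e. perform a paired-sample t-test").
- **Intervals.** "Means and bootstrap-based bias-corrected confidence intervals will be computed for each assessment time of each specified measure".
- **Importance threshold.** "Here again we define as clinically important any departure from zero in the hypothesized direction that is greater than one standard deviation of paired differences".

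Section D.6 describes the UKU grading: "Each treatment emergent symptom is defined on a four-point scale of intensity (0 = not present; 3 = severe"). The only power statement, under Hypothesis #1, is well over 80% at α = 0.05 with 30 patients for an effect of one SD. Sidedness is not given.

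**The concern.** A tolerability aim needs an answer to the question: how much worse could cannabis be than placebo, given these data? None of the four elements gives it. The t-test shows only whether the mean difference is distinguishable from zero. The intervals describe each mean separately; in a crossover, the precision of the within-patient contrast cannot be read from them. The one-SD rule is a cut-off on the point estimate, so it says nothing about what the data exclude.

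The rule also behaves badly for uncommon, severe symptoms. Its yardstick is the SD of the paired differences, and a few high scores enlarge that SD together with the mean. Serious reactions concentrated in a minority of patients can therefore fall well short of the threshold. The Overview says that short-term safety will be stressed, so this is a main output of the trial.

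**Working it through.** **The plan's own figure.** Paired t-test, n = 30, effect d = 1 SD, α = 0.05: noncentral t with 29 degrees of freedom and noncentrality d√n = √30 = 5.48. Power is 99.96% two-sided and 99.99% one-sided, so well over 80% reproduces. It is stated for Hypothesis #1 only.

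**Inputs for the illustration.** n = 30 (Section D.8); UKU grades 0 to 3 (Section D.6); α = 0.05. Assumed: one item and one score per product, k patients with 3 on cannabis and 0 on placebo, and all others 0 on both.

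**Formulas.** Mean difference = 3k/30. SD = 3√[k(30−k)/(30×29)]. Hence mean/SD = √[29k/(30(30−k))] and t = √30 × mean/SD = √[29k/(30−k)]. The grade 3 cancels: under these assumptions neither the test nor the one-SD rule depends on how severe the reaction is.

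| k of 30 | mean/SD | t | p two-sided | p one-sided |
|---|---|---|---|---|
| 1 | 0.18 | 1.00 | 0.33 | 0.16 |
| 2 | 0.26 | 1.44 | 0.16 | 0.080 |
| 3 | 0.33 | 1.80 | 0.083 | 0.042 |
| 4 | 0.39 | 2.11 | 0.043 | 0.022 |
| 15 | 0.98 | 5.39 | <0.001 | <0.001 |
| 16 | 1.05 | 5.76 | <0.001 | <0.001 |

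By the protocol's rule, severe reactions in 15 of 30 patients on cannabis and none on placebo would still not be clinically important; 16 are needed.

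**What an interval for the contrast would add, k = 3.** Mean 0.30, SD 0.915. A 95% t-interval, as a stand-in for the bootstrap, is 0.30 ± 2.045 × 0.915/√30 = 0.30 ± 0.34, or −0.04 to 0.64 points. Divided by 3, that is a risk difference of 10 points (−1.4 to 21.4). The exact (Clopper-Pearson) 95% interval for 3/30 on cannabis is 2.1% to 26.5%.

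**No events, k = 0.** The upper limit for the true rate is 1 − 0.05^(1/30) = 9.5% (one-sided 95%) or 1 − 0.025^(1/30) = 11.6% (two-sided 95%).

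**Continuous scores.** The 95% half-width for the mean contrast is 2.045/√30 = 0.37 SD of paired differences. An estimate just under the one-SD threshold is therefore compatible with up to about 1.37 SD.

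**Sensitivity of the illustration.** With two further patients scoring 1 on cannabis only, besides k = 3: mean 0.367, SD 0.928, t = 2.16, two-sided p = 0.039. The estimate is still only 0.40 SD.

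**The case against.** Several objections have force.

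- **The significance result is not fixed by the plan.** A reader might infer that 3 severe reactions in 30 would simply be declared non-significant. That holds only for a two-sided test with every other difference exactly zero. The hypothesis is directional, the one-sided p is 0.042, and two mild extra cases reverse the two-sided result. The UKU is also rated after three sessions per phase, and Section D.8 does not say it is tested item by item. The example is illustrative only.
- **The protocol never says that a null result means tolerated.** A reader might infer this from Aim #2, but Hypothesis #2 predicts harm and no sentence draws that conclusion. What stands is that the plan neither prevents that reading nor supplies the quantity that would correct it.
- **The t-test need not be the wrong tool.** In the 3 versus 0 example an exact McNemar test gives p = 2 × 0.5³ = 0.25. It needs 6 versus 0 (p = 2 × 0.5⁶ = 0.031) for two-sided significance, so replacing the t-test would lose sensitivity here.
- **Section D.4 does not promise precision for rare events.** "The use of the placebo control will also enable accurate estimates of the side effects of smoked cannabis" explains why a placebo is used. The 0-of-30 limit applies to any group of 30 and is no error in that sentence.
- **Reactions are captured elsewhere.** The schedule lists adverse events, the UKU grades severity and relatedness, and Sections D.5 and E require immediate reporting. These collect and escalate reactions; none compares the products or bounds a difference.
- **An analysis plan not shown may add tables, and an interval can be derived from the mean, SD and n.** Both are fair, and missing symptom tables are not the point. But Section D.8 itself selects the response, the test, the intervals and the importance threshold. It places the intervals on another quantity and sets a threshold unsuited to harm.

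**Conclusion.** The concern holds in limited form. Section D.8 fixes how harm is judged, and none of the stated quantities bounds the cannabis-minus-placebo harm. The one-SD rule is the firmest part: on a 0-versus-3 item, 3 of 30 severe reactions are 0.33 SD and 16 of 30 are needed to exceed the threshold, whatever the sidedness of the test. The p-values (0.083 two-sided, 0.042 one-sided) are secondary.

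These figures assume a single UKU item, one score per product and zeros for everyone else; other patterns change them. The absence of an interval for the tested contrast depends on none of these assumptions. The documents do not support going further, to say that the t-test must be abandoned or that the trial plans to present a null test as proof of tolerability.

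**What to change.** In Section D.8, Hypothesis #2:

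1. Keep the paired t-test and state its sidedness.
2. Compute the bias-corrected bootstrap interval, resampling patients, for the per-patient cannabis-minus-placebo contrast of each measure. Base the tolerability statement on its harm-side limit.
3. State that a non-significant result, or one below one SD of paired differences, is not evidence of tolerability.
4. For the UKU, also report the number and proportion of patients with each symptom (any grade, and grade 3) on each product, with exact 95% intervals. Present this as estimation, not as a replacement significance test. For sparse items these counts are more informative than a bootstrap of the mean, which moves in steps of 3/30 = 0.1 in the example. Note that 0 of 30 leaves rates up to 9.5% (one-sided) or 11.6% (two-sided) not excluded.

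Section D.4 needs no change. The cost is some wording and a little extra analysis of data already collected, with no added patients or visits. The drawback for the investigators is a less favourable safety statement.
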